5.4	Adherence Assessment	11
6	STUDY PROCEDURES	11
6.1	Schedule of Evaluations.....	12
6.2	Description of Evaluations.....	13
6.2.1	Screening Assessment.....	13
6.2.2	Baseline Assessment.....	13
6.2.3	Module Assessment	13
6.2.4	Final Assessment	13
7	SAFETY ASSESSMENTS	14
7.1	Potential Risks and Benefits for Participation	14
7.2	Adverse Event (AE) and Serious Adverse Event (SAE) Collection and Reporting	14
7.2.1	AE/SAE Definitions.....	14
7.2.2	Classification of Severity and Study Relatedness.....	15
7.2.3	AE/SAE Reporting.....	16
8	INTERVENTION DISCONTINUATION.....	16
9	STATISTICAL CONSIDERATIONS	17
9.1	General Design Issues.....	17
9.2	Sample Size and Randomization	17
9.3	Interim analyses and Stopping Rules	17
9.4	Outcomes	17
9.4.1	Primary outcome.....	17
9.4.2	Secondary outcomes	18
9.5	Data Analyses	18
10	DATA COLLECTION AND QUALITY ASSURANCE	18
10.1	Data Collection Forms	18
10.2	Data Management	18
10.3	Quality Assurance.....	19
10.3.1	Training.....	19
10.3.2	Quality Control Committee.....	19

10.3.3	Metrics	19
10.3.4	Protocol Deviations.....	19
10.3.5	Monitoring	19
11	PARTICIPANT RIGHTS AND CONFIDENTIALITY	19
11.1	Institutional Review Board (IRB) Review.....	19
11.2	Informed Consent Form.....	20
11.3	Participant Confidentiality	20
11.4	Study Discontinuation.....	20
12	ETHICAL CONSIDERATIONS.....	20
13	COMMITTEES.....	21
14	PUBLICATION OF RESEARCH FINDINGS	21
15	REFERENCES.....	21
16	SUPPLEMENTS/APPENDICES	24

I. Outcome Measures

II. Informed Consent Form

PRÉCIS

Study Title

Virtual Training for Latino Caregivers to Manage Symptoms of Dementia

Objectives

The objectives of this study are to: (1) culturally and linguistically adapt the STAR-VTF online training modules for Latino caregivers of people living with dementia (PLWD), (2) pilot test Latino caregivers’ responses to the adapted online training modules, and (3) develop a REDCap survey to pragmatically collected caregiver outcomes in a future study.

Design and Outcomes

The study will use a single-arm pilot trial design with Latino caregivers of PLWD. We will assess self-reported outcomes at baseline and 6-8 weeks post-enrollment using a REDCap survey. Outcome measures will include the Revised Memory and Problem Behavior Checklist and Preparedness for Caregiving Scale. In addition, we will assess caregivers’ perceived usability of the online training modules, and we will conduct

qualitative interviews 6-8 weeks post-enrollment. The interviews will assess caregiver satisfaction with and acceptability of the adapted online training modules.

Interventions and Duration

For 6-8 weeks, caregivers will complete online training modules asynchronously. They will access the modules via email or text message. There are 7 online training modules. Caregivers will be instructed to complete one module per week. The content of the modules is as follows: Module 1 provides an understanding and overview of dementia; Module 2 introduces caregivers to the behavioral treatment of dementia, realistic expectations, and effective communication; Module 3 covers the ABC (antecedents, behaviors, consequences) approach to problem-solving, including rationale and development of an ABC plan; Module 4 instructs caregivers to review the ABC plan and revise as needed; Module 5 covers pleasant events and managing negative thinking; Module 6 instructs caregivers to review the ABC plan, pleasant activities schedule, and to revise as needed; Module 7 covers coping with caregiving and maintaining gains. Each module takes about 15 minutes to complete. The modules use text, pictures, and illustrations with a voiceover presentation. Caregivers will receive the online training modules in their preferred language (English or Spanish). They will also receive a workbook to accompany the lessons. The total length of time each caregiver will be in the study is approximately 8 weeks.

Sample Size and Population

Participants will: be aged 18 years or older, live with PLWD or within 5 miles, provide at least 8 hours of care per week, provide care to PLWD who lives at home, and self-identify as Hispanic/Latino. We expect to enroll up to 20 participants. The primary objective of this study is to pilot test the adapted online training modules. Therefore, it is not powered to detect an effect of the intervention.

STUDY TEAM ROSTER

Principal Investigator: [name], MS, MS

Hans Rosling Center for Population Health: Department of Health Services
[name]
[name]
[name]
[contact]
[contact]

1 STUDY OBJECTIVES

1.1 Primary Objective

This pilot study is not testing hypotheses.

1.2 Secondary Objectives

The objectives of this study are to: (1) culturally and linguistically adapt the STAR-VTF online training modules for Latino caregivers of PLWD, (2) pilot test Latino caregivers' responses to the adapted online training modules, and (3) develop a REDCap survey to pragmatically collected caregiver outcomes in a future study.

2 BACKGROUND AND RATIONALE

2.1 Background on Condition, Disease, or Other Primary Study Focus

Latinos are more likely to develop Alzheimer's disease and related dementias (ADRD). Driven by the growing population of older Latino adults in the U.S., the number of Latino PLWD is projected to increase more than nine fold from 379,000 in 2012 to 3.5 million by 2060.¹ Older Latino adults have a higher incidence and prevalence of ADRD compared to older White adults.² These differences are due in large part to the health conditions (e.g., diabetes) and socioeconomic factors (e.g., chronic exposure to economic and social adversity, lower levels and quality of education, and discrimination) that are more prevalent in Latino populations and that are associated with cognitive decline.^{3,4} Despite Latinos being 1.5 times more likely to develop ADRD than White adults,² there is currently a lack of culturally-competent, accessible, and scalable interventions for Latino families.

Latino PLWD have a higher prevalence of behavioral and psychological symptoms of dementia (BPSD) and their caregivers have a higher risk of depression, yet they remain underrepresented in research. Among community-dwelling PLWD, the prevalence of BPSD is higher among Latinos compared to White people, even after adjusting for age, gender, education, income, cognitive and functional status, and caregiver characteristics.⁵ Prevalence of behavior problems in older adults is positively associated with caregiver burden and depression.⁶ Furthermore, behavior problems play a larger role in predicting caregiver burden and depression than do the physical and cognitive impairments of older adults, hours per week providing care, number of care tasks, and duration in the caregiver role. Latino caregivers of PLWD are at higher risk for and have higher levels of depression compared to White caregivers.⁷⁻¹¹ Despite these disparities, Latinos are continually underrepresented in dementia research. Dozens of interventions for managing BPSD in PLWD and for improving the well-being of their caregivers have been developed and tested in the U.S.¹² However, these interventions have been tested predominantly with White caregivers. To address ethnic disparities in health and research, a pragmatic trial design must include the recruitment of Latino caregivers of PLWD.

Latinos experience worse quality of care and discrimination when accessing ADRD care. Compared to White people, Latinos are less satisfied in their communication with healthcare providers, are more likely to perceive that providers fail to provide needed information, and are more likely to report having a problem understanding healthcare providers.¹³⁻¹⁵ Spanish-speaking Latinos report much worse experiences with healthcare than White people.^{13,15-17} In a national survey, nearly 60% of Latino caregivers of PLWD report having faced discrimination when navigating healthcare settings for PLWD.¹⁸ For 85% of Latino caregivers in the survey, it was important that healthcare providers treating ADRD understand their ethnic background, but less than 60% felt confident about having access to culturally-competent healthcare. Our preliminary work indicates that providers miss opportunities to identify Latino caregivers that need supportive services for managing BPSD. Barriers include caregiver-provider language discordance and differences in communication styles, particularly as it relates to the topic of BPSD. For this reason, culturally and linguistically adapting evidence-based interventions, like STAR-VTF, is a critical aspect in the design of pragmatic trials.

Latino caregivers face barriers in seeking ADRD healthcare. Like other minority caregivers of PLWD, Latinos tend to attribute memory loss to normal aging, normalize behavioral and psychological symptoms, and hide problems with symptoms to avoid stigmatization of their family member.¹⁹ This stems from the lack of culturally- and linguistically-competent information about dementia that is available in these communities, rather than from culturally-influenced beliefs. The normalization of symptoms and the stigmatization of the disease is a major barrier to seeking ADRD healthcare. Other major barriers for Latino caregivers include clinicians' lack of knowledge about the differences between normal aging and early signs of dementia, lack of Spanish-speaking clinicians, and experience of discrimination in healthcare settings.¹⁸⁻²⁰ Our preliminary work indicates that Latino caregivers hesitate to raise concerns about BPSD with healthcare providers due to language discordance and health literacy factors. Interventions such as STAR-VTF embedded in healthcare systems can help to raise Latino caregivers' awareness about the availability of culturally-competent, nonpharmacological treatments for improving management of BPSD at home.

STAR-VTF is an evidence-based virtual intervention to support caregivers in managing BPSD. STAR-C Virtual Training and Follow-up (STAR-VTF) is a virtual adaptation of a systematic and standardized behavioral approach – known as the Seattle Protocols – to training caregivers to reduce BPSD in community-dwelling PLWD. The Seattle Protocols teach caregivers the ABCs of behavior change – a process that involves identifying specifics about the problem under consideration, identifying possible environmental or interpersonal factors that lead up to and sustain their occurrence, and systematically altering those factors to reduce problems.²¹ The Seattle Protocols were consolidated into the STAR-C program wherein coaches (master's degree or equivalent in

psychology, social work, or a related field) visit caregivers at home to deliver the training.²² The condensed 6-week program involves 4 in-home sessions and 2 telephone sessions.^{23,24} A randomized controlled trial was conducted to compare STAR-C to routine medical care in English-speaking, predominantly White participants.²³ The study population included only 1 Latino caregiver (randomized to control arm). At 6 months, caregivers randomized to the intervention arm had significantly lower depression, subjective burden, and caregiver reaction scores.

To ease translation, STAR-VTF was developed and is now being tested in a pragmatic trial at Kaiser Permanente Washington (KPWA).^{25,26} STAR-VTF delivers the same content as STAR-C but in an entirely virtual environment.²⁶ For 6-8 weeks, caregivers complete 6 online training modules asynchronously and have 6 30-minute weekly telephone check-ins with a coach (social worker or mental health counselor). The 6 modules cover the same content as STAR-C (Table 1). The modules are hosted on the Kaiser Permanente School of Allied Health Sciences learning management system. Currently, only caregivers participating in the ongoing pragmatic trial at KPWA have access to this website. Our preliminary data identified potential areas of misfit between STAR-VTF and Latino caregivers. The modules: do not sufficiently address dementia literacy, use language/semantics that could be insensitive, and do not reflect Latino cultural values that could influence family structures and views of caregiving.

Table 1. STAR-VTF Modules	
1	Introduction to behavioral treatment of dementia, realistic expectations, & effective communication
2	ABC approach to problem-solving, including rationale & development of an ABC plan
3	Review of ABC plan and revise if needed
4	Increasing pleasant events & managing negative thinking
5	Review of ABC plan, pleasant events schedule, & revise if needed
6	Coping with caregiving and maintaining gains

Table 2. Adapted STAR-VTF Modules	
1	Understanding and overview of dementia
2	Introduction to behavioral treatment of dementia, realistic expectations, & effective communication
3	ABC approach to problem-solving, including rationale & development of an ABC plan
4	Review of ABC plan and revise if needed
5	Increasing pleasant events & managing negative thinking
6	Review of ABC plan, pleasant events schedule, & revise if needed
7	Coping with caregiving and maintaining gains

2.2 Study Rationale

We conducted qualitative interviews with 44 stakeholders (e.g., Latino caregivers, frontline clinicians, and health educators). The stakeholders were not involved in the ongoing STAR-VTF pragmatic trial at KPWA and only viewed prototypes of the modules. Our analysis revealed that healthcare systems are not providing adequate education about dementia and support in managing BPSD. In fact, most Latino caregivers were unaware that healthcare providers could help with this matter. Stakeholders expressed interest in STAR-VTF, but there were concerns with particular aspects of the modules. Based on feedback from stakeholders, we have identified three adaptations to the STAR-VTF modules that would better serve Latino caregivers.

Increase knowledge about dementia to reduce normalization of symptoms and stigmatization of PLWD. Similar to other studies of racial and ethnic minority caregivers, our preliminary data reveal that Latinos tend to: believe dementia is a normal part of aging; attribute behavioral and psychological symptoms to normal aging or to their family member's personality; attribute the development of dementia to emotions; believe that dementia is a mental health disorder, and therefore, perceive PLWD as being *loco* (crazy); view pharmacological treatment of BPSD as accepting that their family member is *loco* (crazy); and believe that dementia can be healed or its symptoms managed through herbal remedies, praying, and therapy.

Module 1 includes a 7-minute section titled "Overview of Dementia." It covers the links between dementia and behavior, common causes of dementia, how dementia affects a person's ability to do daily tasks, and how changes in behavior are progressive and not intentional. The first adaptation of our proposed study will be to expand the content in this section. The goal is to reduce normalization of BPSD and the stigma associated with AD/DRD. For example, when discussing common causes of dementia, we will add content about the differences between normal age-related forgetfulness and serious memory problems. We will also explain that dementia is a physical (not mental) illness.

Eliminate stigmatizing, offensive, and culturally irrelevant language. We found that Latinos tend to prefer the term *pérdida de la memoria* (memory loss) instead of "Alzheimer's disease" or "dementia." Furthermore, stakeholders were concerned with program materials describing behavior symptoms as "challenging," "problematic," and "bothersome." It could be misinterpreted as describing PLWD (as opposed to their symptoms). In addition, stakeholders explained that Latinos tend to place the needs of the person they are caring for over their own needs. It is a way of expressing the Latino cultural value of *familismo* (familism). Thus, stakeholders strongly advised against program materials describing caregiving as burdensome. Finally, Latinos rarely identified with the label "caregiver." The translated word (*cuidador*) does not appear to be commonly-used. It is sometimes misinterpreted to refer to a formal caregiver or to an informal/family caregiver who gets paid to provide care. Latino caregivers we interviewed preferred to simply use kinship terms (e.g., daughter, daughter-in-law, wife of person with memory loss) to describe their role.

Based on these findings, the second adaptation of our proposed study will be to revise the language used across all modules. The goal is to eliminate any language that could be stigmatizing, offensive, and culturally irrelevant. For example, we will replace “dementia” with “memory loss,” eliminate negative descriptions of BPSD, avoid the term “caregiver burden,” and replace the label “caregiver” with kinship terms.

Incorporate Latino family structure and the nature of caregiving in Latino families. Stakeholders stressed the importance of targeting the family unit, as opposed to a primary caregiver, in ADRD healthcare for Latinos. A bilingual and bicultural social worker said, “It's not necessarily just one person [caring for PLWD]. Because our families come in packs... I think being able to be flexible in some of the norms that an education program will have, whether that means two people or more -- because usually, it's a family.” In the vast majority of cases, Latino caregivers we interviewed described receiving extensive support from family members (including small children). They lived in multigenerational households or within close proximity of relatives, facilitating frequent help with care responsibilities and emotional support. In addition, there was a strong aversion to using formal respite services, driven by cultural, language, and economic factors.

In module 7, caregivers learn that enlisting the help of family members and formal respite care providers could help them better cope with caregiving. It assumes most caregivers live alone with PLWD and that other family members provide minimal support. The third adaptation of our proposed study is to incorporate content that reflects the structure of Latino families (i.e., multigenerational households, living near family) and how caregiving is often a shared responsibility within the family unit. Furthermore, when suggesting use of formal respite care services, we will be sensitive to culturally-influenced preferences. We will also address concerns about the lack of bilingual, bicultural, and affordable services.

Intervention Regimen: For 6-8 weeks, caregivers will complete the 7 online training modules asynchronously. They will access the video modules sent to them through text message or email. As described in Table 2, the content of the modules includes an overview of dementia, realistic expectations, effective communication, using the ABC approach to problem-solve BPSD, and planning pleasant events. Each module takes about 15 minutes to complete. The modules use text, pictures, and illustrations with a voiceover presentation. They will also receive a printed workbook to go along with the lessons. ***While the STAR-VTF intervention incorporates a coaching component, the present study will only pilot test the adapted online training modules.*** The full STAR-VTF intervention – adapted modules coupled with coaching – will be tested in a future study with Latino caregivers.

3 STUDY DESIGN

Objective 1: Culturally and linguistically adapt the STAR-VTF online training modules for Latino caregivers of PLWD

Findings from our stakeholder interviews indicate that no major changes to the intervention’s core components are required. Instead, we need to improve the content and

language used in the online training modules. The first adaptation will be to expand the content in the “Overview of Dementia” section of module 1. The content will address common beliefs and attitudes about dementia that result in families normalizing dementia symptoms and stigmatizing PLWD. The second adaptation will be to revise the language across all modules. We will eliminate any language that stakeholders suggested could be stigmatizing, offensive, and culturally irrelevant. We will rewrite the content to a 6th grade or lower reading level – a suggestion made by frontline clinician and health educator stakeholders. The content of the modules will be translated and the voiceover presentations recorded in Spanish. The third adaptation will be to incorporate content into module 7 that reflects the structure of Latino families (e.g., tendency to live multigenerational households) and how caregiving can often be a shared responsibility within the family unit.

The PI will lead this adaptation work with support from the study’s staff member. Feedback on draft adaptations will be obtained from stakeholders, including Latino caregivers of PLWD and Spanish-English bilingual and bicultural health educators. These individuals are members of a community advisory board. We will refine adaptations based on stakeholder feedback.

Objective 2: Pilot test Latino caregivers’ responses to the adapted online training modules

The study will use a single-arm pilot trial design. Participants will be up to 20 caregivers of PLWD. We will target individuals who are: aged 18 years or older, live with PLWD or within 5 miles, provide at least 8 hours of care per week, provide care to PLWD who lives at home, and self-identify as Hispanic/Latino.

Caregivers will complete a baseline survey using a REDCap link that will be delivered to caregivers via email or text message. The survey will include sociodemographic characteristics and the outcome measures (i.e., Revised Memory and Problem Behavior Checklist and Preparedness for Caregiving Scale). We will collect outcome measures from caregivers again 6-8 weeks post-enrollment using the same data collection method. Sociodemographic characteristics will include: caregiver age, occupational status, whether caregiver works outside of the home, number of people living in caregiver’s home, educational attainment, English fluency, preferred language, languages spoken at home, race, gender, annual household income, device ownership, Internet access at home, health insurance status of caregiver and PLWD, relationship to PLWD, age of PLWD, gender of PLWD, number of years in caregiving role, whether caregiver lives in same household as PLWD, and hours per week providing care.

After completing the baseline survey, caregivers will begin participation in the intervention. ***The intervention tested in this study will only involve the self-directed training component of the STAR-VTF intervention.*** We will provide caregivers with the video modules via text message or email. We will also mail each participant a copy of the adapted version of the STAR-VTF workbook in their preferred language. There are handouts and resources to along with each lesson. Caregivers will be instructed to complete 1 module per week for 7 weeks (Table 2).

After 6-8 weeks, we will schedule an exit interview with caregivers. The interview will happen virtually (phone or videoconferencing) and will be under 1 hour. We will ask participants semi-structured questions to understand their experience with the online training modules and with completing the survey via REDCap.

Objective 3: Develop a REDCap survey to pragmatically collected caregiver outcomes. We will create a REDCap survey that will facilitate collection of caregiver outcomes pragmatically in a larger pilot study and full-scale embedded pragmatic clinical trial that we plan to conduct in the future. The REDCap instrument will include the English and Spanish versions of the Revised Memory and Problem Behavior Checklist and the Preparedness for Caregiving Scale. In the future, this functionality will allow remote collection of caregiver outcomes that can be securely linked back to the patient electronic medical record – solving the issue with health information management laws that make it difficult or impossible to collect caregiver outcomes as part of a patient’s electronic medical record. In the present study, we will pilot the REDCap survey by asking caregivers to complete it at baseline and 6-8 weeks post-enrollment.

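### The final survey, and in the Précis the exit interview, may fall before module 7: the window opens on day 42, the seventh module week runs from day 42 to day 49 plus any start lag, and no rule links them

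*Combined protocol and SAP*

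**What the plan says.** **Final survey.** Section 3 (Objective 2) states: "We will collect outcome measures from caregivers again 6-8 weeks post-enrollment using the same data collection method". The Précis agrees: "We will assess self-reported outcomes at baseline and 6-8 weeks post-enrollment using a REDCap survey". Section 3 (Objective 3) and Section 9.4.1 give the same window. Section 6.2.4 places the survey after 6-8 weeks from enrollment. The Section 6.1 table puts the final assessment in Weeks 7-8.

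**Exit interview.** The Précis also sets it at 6-8 weeks post-enrollment and gives its purpose: "The interviews will assess caregiver satisfaction with and acceptability of the adapted online training modules". Section 3 says: "After 6-8 weeks, we will schedule an exit interview with caregivers", and names no starting point for the count.

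**Modules.** Section 3 says: "After completing the baseline survey, caregivers will begin participation in the intervention". The pace is also set there: "Caregivers will be instructed to complete 1 module per week for 7 weeks (Table 2". Under Section 6.2.1, enrollment begins when staff receive the signed e-consent. Section 6.2.2 sends the baseline survey after that.

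**Link between the two.** No section makes the end of module 7 a condition for the survey or interview. Section 5.4 tracks completion rates, and Section 10.3.3 logs when surveys were prompted and interviews scheduled.

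**The concern.** Two clocks run side by side. The assessment clock starts at enrollment. The module clock starts later, after the baseline survey, and the instructed course lasts seven weeks. If the assessment window opens at six weeks, staff who follow the protocol exactly may survey or interview a caregiver who is on schedule but has not yet reached module 7.

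Module 7 carries the third adaptation, on family structure and shared caregiving (Section 3, Objective 1). Objective 2 is to pilot responses to the adapted modules, and Section 9.4.2 makes the exit interview the source on acceptance. An interview held before module 7 cannot cover that content. Caregivers who fall behind will bring mixed exposure to any fixed date. The avoidable part is the extra mixing that comes only from an early contact.

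**Working it through.** **Inputs.** Window of 6-8 weeks from enrollment (Précis; Section 3; Section 9.4.1). Seven modules at one per week (Section 3; Table 2). Module start on day L, counting enrollment as day 0. L is not stated. Section 6.1 puts enrollment and baseline in Week 0, so I assume 0-7 days.

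**The plan's own figure.** 7 modules × 1 week = 7 weeks = 49 days, which agrees with Section 3.

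**Window.** 6 × 7 = day 42 to 8 × 7 = day 56, which is 15 days counted inclusively.

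**Date of module 7.** The protocol does not say when in its week a module is done, so I bracket it:
- First-day pace: 6 × 7 + L = 42+L, giving day 42, 45 or 49 at L = 0, 3 or 7.
- End-of-week pace: 7 × 7 + L = 49+L, giving day 49, 52 or 56.

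**Modules done on day 42.**
- End-of-week pace, floor((42−L)/7): 6 at L = 0 and 5 at L = 1-7.
- First-day pace, floor((42−L)/7)+1: 7 at L = 0 (module 7 on that same day) and 6 at L = 1-7.

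**Window days before module 7.** The table's Weeks 7-8 can be counted in three ways. If Week 0 is days 0-6, Week 7 starts on day 49 and Week 8 ends on day 62. If Week 1 is days 1-7, they are days 43-56. As elapsed weeks they are days 49-56.

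| Reading | Window | First-day pace, L = 0, 3, 7 | End-of-week pace, L = 0, 3, 7 |
|---|---|---|---|
| 6-8 weeks post-enrollment | days 42-56 (15) | 0, 3, 7 | 7, 10, 14 |
| Weeks 7-8, Week 0 = days 0-6 | days 49-62 (14) | 0, 0, 0 | 0, 3, 7 |
| Weeks 7-8, Week 1 = days 1-7 | days 43-56 (14) | 0, 2, 6 | 6, 9, 13 |
| Weeks 7-8, elapsed | days 49-56 (8) | 0, 0, 0 | 0, 3, 7 |

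Each entry counts the days from the opening of the window up to, but not including, day 42+L or day 49+L. For example, at L = 3 and end-of-week pace, days 42 to 51 give 10 days.

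A lag of up to 7 days is consistent with the table's Week 0, but nothing in the documents guarantees it. For L above 7, the plain window closes (day 56) before the seventh module week ends. At L = 14 that week ends on day 63.

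**Table heading.** Section 6.1 places the module assessments in Weeks 1-6, which is six weekly slots for seven weekly modules.

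**The case against.** The best reply is that the timing works on a fair reading. The modules are asynchronous and take about 15 minutes, so a prompt caregiver may finish module 7 on the first day of its week. With no lag that is day 42, and nothing is missed. The table gives Weeks 7-8, and two of its three readings leave no overlap at that pace for any lag up to 7 days. In Section 3 the interview sentence comes soon after the seven-week instruction, so it can be read as after the course, and it says when scheduling happens, with the interview following later. If after 6-8 weeks means day 56 or later, there is no conflict for L up to 7, since 49 + 7 = 56. An early interview would still cover the first adaptation (module 1) and much of the second (all modules), and the advisory board reviews the draft adaptations in any case.

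Most of this stands as a limit on size. It does not supply the missing rule. The Précis, Section 3 (both survey statements) and Section 9.4.1 set the survey at 6-8 weeks, not after them, and the Précis puts the interview on the same clock. The later-contact wording allows a later date without requiring one. The table agrees with the plain window on one reading and opens a week later on the others, so it needs reconciling too.

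**Conclusion.** The point holds and is minor. The stated window can place the survey, and under the Précis the interview, before module 7, and no section prevents this. I am confident of the day counts and of the missing link. The size is uncertain: it depends on the lag (assumed 0-7 days), the pace within each week and how weeks are counted. It runs from no overlap to 14 of 15 window days. These are not proportions of caregivers, and the documents give no basis for estimating that share. The study has at most 20 caregivers, tests no hypothesis (Sections 1.1 and 9.1) and uses descriptive and qualitative analysis only (Section 9.5), so no inference is at risk.

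A reader might infer more than the documents support:
- *That final assessments will generally precede module 7.* The window also contains later days, and several readings leave little or no overlap.
- *That usability data for module 7 will be lost.* Sections 6.2.3 and 9.4.2 trigger the usability scale after every module, so the Weeks 1-6 heading is a table error.
- *That the window was carried over by mistake from the parent programme.* Section 2.1 says of it: "For 6-8 weeks, caregivers complete 6 online training modules asynchronously". Six weekly modules would end on day 42, which fits, but the documents do not say that this is the origin.

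**What to change.** Change assessment timing only.

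1. Reconcile the Précis, Section 3 (Objectives 2 and 3), Section 6.1, Section 6.2.4 and Section 9.4.1 to one final-assessment window for both survey and interview. It should open at least seven full weeks after the date on which the caregiver is first given the modules.
2. Log that date. The Précis and Section 3 send modules by text or email, while Section 5.2 describes a login website, so the text should say which event counts. The log in Section 10.3.3 can hold it.
3. Apply the window to every caregiver, whatever number of modules they have completed, so that completers are not selected.
4. Correct the Weeks 1-6 heading in Section 6.1 so that it covers all seven modules.
5. Report modules completed by the survey date if the learning-system data are dated. Section 5.4 promises only completion rates, so otherwise ask at the exit interview.

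**Cost.** A wording amendment with IRB review (Section 11.1), a changed survey send date and one logged date. Counted from enrollment, the window would open on day 49, 52 or 56 at L = 0, 3 or 7. That leaves 8−L = 8, 5 or 1 days up to and including day 56. The Précis states: "The total length of time each caregiver will be in the study is approximately 8 weeks". Participation may run slightly past that where module access is delayed.
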